9.5.2.2 Description of Procedures/Assessments Schedule

Please refer to the Schedule of Procedures/Assessments ([Table 7](#) and [Table 8](#)).

9.5.3 Appropriateness of Measurements

All clinical assessments are standard measurements commonly used in studies of solid tumors.

The safety assessments to be performed in this study, including hematology analyses, blood chemistry tests, urinalysis, ECGs/echocardiograms, and assessment of AEs, are standard evaluations to ensure subject safety. The use of RECIST 1.1 for tumor assessments of solid tumors is widely accepted (see [Appendix 1](#)) ([Eisenhauer, et al., 2009](#)).

9.5.4 Reporting of Serious Adverse Events, Pregnancy, and Events Associated with Special Situations

9.5.4.1 Reporting of Serious Adverse Events

All SERIOUS ADVERSE EVENTS, regardless of their relationship to study treatment, must be reported on a completed SAE form by email or fax as soon as possible but no later than 1 business day (or 24 hours for EU sites) from the date the investigator becomes aware of the event.

Serious adverse events, regardless of causality assessment, must be collected through the last visit. All SAEs must be followed to resolution or, if resolution is unlikely, to stabilization. Any SAE judged by the investigator to be related to the study treatment or any protocol-required procedure should be reported to the sponsor regardless of the length of time that has passed since study completion.

The detailed contact information for reporting of SAEs is provided in the Investigator Study File.

For urgent safety issues, please ensure all appropriate medical care is administered to the subject and contact the appropriate study team member listed in the Investigator Study File.

It is very important that the SAE report form be filled out as completely as possible at the time of the initial report. This includes the investigator's assessment of causality.

Any follow-up information received on SAEs should be forwarded within 1 business day of its receipt. If the follow-up information changes the investigator's assessment of causality, this should also be noted on the follow-up SAE form.

Preliminary SAE reports should be followed as soon as possible by detailed descriptions including copies of hospital case reports, autopsy reports, and other documents requested by the sponsor.

The investigator must notify his/her IRB/IEC of the occurrence of the SAE in writing, if required by their institution. A copy of this communication must be forwarded to the sponsor to be filed in the sponsor's Trial Master File.

9.5.4.2 Reporting of Pregnancy and Exposure to Study Drug Through Breastfeeding

Any pregnancy in which the estimated date of conception is either before the last visit or within 28 days of last study treatment, or any exposure to study drug through breastfeeding during study treatment or within 28 days of last study treatment, must be reported.

If an adverse outcome of a pregnancy is suspected to be related to study drug exposure, this should be reported regardless of the length of time that has passed since the exposure to study treatment.

A congenital anomaly, death during perinatal period, an induced abortion, or a spontaneous abortion are considered to be an SAE and should be reported in the same time frame and in the same format as all other SAEs (see Reporting of Serious Adverse Events [[Section 9.5.4.1](#)]).

Pregnancies or exposure to study drug through breastfeeding must be reported by fax or email as soon as possible but no later than 1 business day from the date the investigator becomes aware of the pregnancy. The contact information for the reporting of pregnancies and exposure to study drug through breastfeeding is provided in the Investigator Study File. The Pregnancy Report Form must be used for reporting. All pregnancies must be followed to outcome. The outcome of the pregnancy must be reported as soon as possible but no later than 1 business day from the date the investigator becomes aware of the outcome.

A subject who becomes pregnant must be withdrawn from the study.

9.5.4.3 Reporting of Events Associated with Special Situations

9.5.4.3.1 REPORTING OF ADVERSE EVENTS ASSOCIATED WITH STUDY DRUG OVERDOSE, MISUSE, ABUSE, OR MEDICATION ERROR

Adverse events associated with study drug overdose, misuse, abuse, and medication error refer to AEs associated with uses of the study drug outside of that specified by the protocol. Overdose, misuse, abuse, and medication error are defined as follows:

Overdose	Accidental or intentional use of the study drug in an amount higher than the protocol-defined dose
Misuse	Intentional and inappropriate use of study drug not in accordance with the protocol
Abuse	Sporadic or persistent intentional excessive use of study drug accompanied by harmful physical or psychological effects

Medication error Any unintentional event that causes or leads to inappropriate study drug use or subject harm while the study drug is in the control of site personnel or the subject.

All AEs associated with overdose, misuse, abuse, or medication error should be captured on the Adverse Event CRF and also reported using the procedures detailed in Reporting of Serious Adverse Events ([Section 9.5.4.1](#)) even if the AEs do not meet serious criteria. Abuse is always to be captured as an AE. If the AE associated with an overdose, misuse, abuse, or medication error does not meet serious criteria, it must still be reported using the SAE form and in an expedited manner but should be noted as nonserious on the SAE form and the Adverse Event CRF.

9.5.4.4 Expedited Reporting

The sponsor must inform investigators and regulatory authorities of reportable events, in compliance with applicable regulatory requirements, on an expedited basis (ie, within specific time frames). For this reason, it is imperative that sites provide complete SAE information in the manner described above.

9.5.4.5 Breaking the Blind

Not applicable

9.5.4.6 Regulatory Reporting of Adverse Events

Adverse events will be reported by the sponsor or a third party acting on behalf of the sponsor to regulatory authorities in compliance with local and regional law and established guidance. The format of these reports will be dictated by the local and regional requirements.

All studies that are conducted within any European country will comply with European Good Clinical Practice Directive 2005/28/EC and Clinical Trial Directive 2001/20/EC. All suspected unexpected serious adverse reactions (SUSARs) will be reported, as required, to the competent authorities of all involved European member states.

9.5.5 Completion/Discontinuation of Subjects

A subject (or subject's parent or guardian) may elect to discontinue the study at any time for any reason. All subjects who discontinue the study are to complete the study's early discontinuation procedures indicated in the Schedule of Procedures/Assessments ([Table 7](#) and [Table 8](#)).

The investigator will promptly explain to the subject involved that the study will be discontinued for that subject and provide appropriate medical treatment and other necessary measures for the subject. A subject who has ceased to return for visits will be followed up by mail, phone, or other means to gather information such as the reason for failure to return, the

status of treatment compliance, the presence or absence of AEs, and clinical courses of signs and symptoms.

Subjects who discontinue early from the study will be discontinued for 1 of these primary reasons: AE(s), lost to follow-up, subject choice, progression of disease, withdrawal of consent, pregnancy, study terminated by sponsor, or other.

9.5.6 Abuse or Diversion of Study Drug

Not applicable

9.5.7 Confirmation of Medical Care by Another Physician

The investigator will instruct subjects (or guardian/legally authorized representative) to inform site personnel when they are planning to receive medical care by another physician. At each visit, the investigator will ask the subject (or guardian/legally authorized representative) whether the subject has received medical care by another physician since the last visit or is planning to do so in the future. When the subject is going to receive medical care by another physician, the investigator, with the consent of the subject (or guardian/legally authorized representative), will inform the other physician that the subject is participating in the clinical study.

9.6 Data Quality Assurance

This study will be organized, performed, and reported in compliance with the protocol, SOPs, working practice documents, and applicable regulations and guidelines. Site audits will be made periodically by the sponsor's or the CRO's qualified compliance auditing team, which is an independent function from the study team responsible for conduct of the study.

9.6.1 Data Collection

Data required by the protocol will be collected on the CRFs and entered into a validated data management system that is compliant with all regulatory requirements. As defined by ICH guidelines, the CRF is a printed, optical, or electronic document designed to record all of the protocol-required information to be reported to the sponsor on each study subject.

Data collection on the CRF must follow the instructions described in the CRF Completion Guidelines. The investigator has ultimate responsibility for the collection and reporting of all clinical data entered on the CRF. The investigator or designee as identified on Form FDA 1572 must sign the completed CRF to attest to its accuracy, authenticity, and completeness.

Completed, original CRFs are the sole property of Eisai and should not be made available in any form to third parties without written permission from Eisai, except for authorized representatives of Eisai or appropriate regulatory authorities.

9.6.2 Clinical Data Management

All software applications used in the collection of data will be properly validated following standard computer system validation that is compliant with all regulatory requirements. All data, both CRF and external data (eg, laboratory data), will be entered into a clinical system.

9.7 Statistical Methods

All statistical analyses will be performed by the sponsor or designee after the study is completed and the database is locked and released. Statistical analyses will be performed using SAS software or other validated statistical software as required. Details of the statistical analyses will be included in a separate statistical analysis plan (SAP).

9.7.1 Statistical and Analytical Plans

Descriptive statistics will be used to summarize study endpoints. Categorical variables will be summarized by number and percentage. Continuous variables will be summarized using n (number of subjects with available data), mean, standard deviation, median, Q1, Q3, and range (minimum and maximum), unless otherwise specified.

Efficacy data will be analyzed using the Evaluable Analysis Set, safety data will be analyzed using the Safety Analysis Set, PK data will be analyzed using the PK Analysis Set, and PD data will be analyzed using the PD Analysis Set. All analyses will be performed by dose level in Phase 1 (if appropriate) and for each study cohort in Phase 2, unless otherwise specified.

9.7.1.1 Study Endpoints

9.7.1.1.1 PRIMARY ENDPOINTS

Primary Endpoints for Phase 1

- MTD and RP2D of lenvatinib in combination with everolimus
- Safety and toxicity of lenvatinib in combination with everolimus

Primary Endpoint for Phase 2

- ORR, defined as the proportion of subjects who have the best overall response (BOR) of complete response (CR) or partial response (PR), at Week 16

9.7.1.1.2 SECONDARY ENDPOINTS

Secondary Endpoints for Phase 1 and Phase 2

- ORR at the time of data cutoff
- DCR, defined as the proportion of subjects who have the BOR of CR or PR or stable disease (SD) (SD duration ≥ 7 weeks since the first dose of the study treatment)
- CBR, defined as the proportion of subjects who have the BOR of CR or PR or durable SD (SD duration ≥ 23 weeks since the first dose of the study treatment)
- DOR, defined as the time from the date of the first documented CR or PR to the date of the disease progression objectively documented or death (whichever occurs first)

- Plasma PK of lenvatinib and trough concentrations of everolimus when administered in combination
- Safety and toxicity of lenvatinib in combination with everolimus in Phase 2

9.7.1.1.3 EXPLORATORY ENDPOINTS

- Assess candidate alterations in genes and/or proteins that may contribute to tumor development and predictive marker of response in archival tumor tissue
- Correlative blood and tumor biomarkers of treatment effects and outcomes

9.7.1.2 Definitions of Analysis Sets

- **Evaluable Analysis Set**, defined as all subjects, who have measurable disease present at baseline and at least 1 post-baseline efficacy assessment, unless they have discontinued prior to the first efficacy assessment due to progressive disease. This will be the analysis set for efficacy.
- **Safety Analysis Set**, defined as all subjects who received at least 1 dose of study drug (lenvatinib or everolimus).
- **Pharmacokinetic (PK) Analysis Set**, defined as subjects in Safety Analysis Set who had at least 1 measurable postdose plasma concentration with an adequately documented dosing history.
- **Pharmacodynamic (PD) Analysis Set**, defined as all subjects in Safety Analysis Set who had evaluable PD data.

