Phase 2 Cohorts 1 to 3 will use a 10+10 Simon's optimal 2-stage design for each cohort; 10 evaluable subjects will be enrolled to each stage. The Sponsor will closely monitor enrollment to ensure that at least 50% of subjects enrolled in each cohort are <18 years of age at the time of informed consent. The primary outcome measure for Ewing sarcoma/pPNET, rhabdomyosarcoma, and HGG will be ORR (complete or partial response) at 16 weeks. If there are no responses among the 10 subjects in Stage 1, then the enrollment to that disease cohort will stop and conclude that the lenvatinib/everolimus combination therapy does not elicit a response in that disease cohort. If there is at least 1 response in the first stage, then the second stage will enroll 10 additional evaluable subjects. If there are 2 or fewer responses among the 20 evaluable subjects, then lenvatinib/everolimus combination therapy will be declared a failure for that disease cohort. Subjects will meet the criteria for being evaluable for an objective response if they have measurable disease present at baseline and at least 1 post-baseline efficacy assessment, unless they have discontinued prior to the first efficacy assessment due to progressive disease. Subjects who are not evaluable for objective response will be replaced.

The Treatment Phase for each subject in Phase 2 ends after completing 4 cycles of treatment unless subject discontinues early. Those subjects who discontinue study treatment before completing 4 cycles transition to the Off-treatment Visit. Those who complete 4 cycles will transition to the Extension Phase. Study treatment and tumor assessments will continue during the Extension Phase.

Dosing Nomogram

The dose nomogram in [Table 3](#) provides the dose of lenvatinib to be administered for BSA increments starting from 0.6 m². BSA must be calculated on Day 1 of each cycle based on the subject's current height and body weight. The actual dose to be administered is rounded to the nearest whole number. The total lenvatinib dose is capped at 18 mg daily (Dose Levels -1 and 1), and at 24 mg (Dose Levels 2 and 3).

Table 3 Total Lenvatinib Dose (mg): Body Surface Area (m²) * Dose Level (mg/m²)

Lenvatinib Dose Levels							
8 mg/m ² Everolimus 3.0 mg/m ² Dose Level -1		11 mg/m ² Everolimus 3.0 mg/m ² Dose Level 1		14 mg/m ² (Everolimus 3.0 mg/m ²) Dose Level 2		14 mg/m ² (Everolimus 4.5 mg/m ²) Dose Level 3	

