9.5.1.5.1 ADVERSE EVENTS

An AE is any untoward medical occurrence in a patient or clinical investigation subject administered an investigational product. An AE does not necessarily have a causal

relationship with the medicinal product. For this study, the study drugs are lenvatinib and everolimus.

The criteria for identifying AEs in this study are:

- Any unfavorable and unintended sign (including an abnormal laboratory finding), symptom, or disease temporally associated with the use of an investigational product, whether or not considered related to the investigational product (Note: Every sign or symptom should not be listed as a separate AE if the applicable disease [diagnosis] is being reported as an AE)
- Any new disease or exacerbation of an existing disease. However, worsening of the primary disease should be captured under efficacy assessments as disease progression rather than as an AE.
- Any deterioration in nonprotocol-required measurements of a laboratory value or other clinical test (eg, ECG or x-ray) that results in symptoms, a change in treatment, or discontinuation of study drug
- Recurrence of an intermittent medical condition (eg, headache) not present pretreatment (Baseline)
- An abnormal laboratory test result should be considered an AE if the identified laboratory abnormality leads to any type of intervention, withdrawal of study drug, or withholding of study drug, whether prescribed in the protocol or not.

All AEs observed during the study will be reported on the CRF. All AEs, regardless of relationship to study drug or procedure, should be collected beginning from the time the subject signs the study ICF through the last visit and for 28 days after the last dose of study treatment. Serious AEs (SAEs) will be collected for 28 days after the last dose of study treatment.

Abnormal laboratory values should not be listed as separate AEs if they are considered to be part of the clinical syndrome that is being reported as an AE. It is the responsibility of the investigator to review all laboratory findings in all subjects and determine if they constitute an AE. Medical and scientific judgment should be exercised in deciding whether an isolated laboratory abnormality should be classified as an AE. Any laboratory abnormality considered to constitute an AE should be reported on the Adverse Event CRF.

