9.7.1.6.1 PRIMARY EFFICACY ANALYSIS

Phase 1

The study will utilize the rolling 6 design. The primary objective of Phase 1 is to determine the MTD and to establish the RP2D.

Phase 2

The primary efficacy endpoint in Phase 2 is ORR at 16 weeks. Objective responses will count only confirmed CR and PR. Estimated ORR and its exact 95% CI using the Clopper-Pearson method will be presented.

9.7.1.6.2 SECONDARY EFFICACY ANALYSES FOR PHASE 1 AND PHASE 2

The secondary efficacy endpoints will be ORR at the time of data cutoff, DCR, CBR and DOR. These endpoints in Phase 1 will be summarized if appropriate and listed by dose level, and ORR will be based on only subjects with measurable disease at screening/baseline. For Phase 2, the ORR, DCR and CBR will be provided with exact 95% CIs using the Clopper-Pearson method. The DOR will be analyzed using Kaplan-Meier approach among the responders (CR or PR). If a subject had no record of disease progression or did not die before the data cutoff date, or before early discontinuation (including discontinuations due to toxicity, undocumented clinical progression, change of cancer treatment, or decreasing performance status), then the subject will be censored at the last available tumor assessment.

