12 APPENDICES

Appendix 1 **Response Evaluation Criteria in Solid Tumors (RECIST) 1.1**

Tumor response assessments in this clinical trial will use Response Evaluation Criteria in Solid Tumors (RECIST 1.1) based on the 2009 article by Eisenhauer et al entitled *New response evaluation criteria in solid tumors: revised RECIST guideline (version 1.1)* ([Eisenhauer, et al., 2009](#)).

The sole modification to RECIST 1.1 to be implemented in this trial is that chest x-rays may not be used to follow disease; only CT scans may be used to follow chest disease. As required by RECIST 1.1, the protocol states that the minimum duration of stable disease is 7 weeks following the date of first dose of study drug.

The Eisenhauer article published in the European Journal of Cancer, is available online at: <http://linkinghub.elsevier.com/retrieve/pii/S0959804908008733>.

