 - Partial Response (PR): Greater than or equal to 50% decrease, compared to baseline, in the sum of products of perpendicular diameters of all measurable enhancing lesions sustained for at least 4 weeks. In the absence of a confirming scan 4 weeks later, this scan will be considered only stable disease. No progression of non-measurable disease. No new lesions. Stable or improved nonenhancing (T2/FLAIR) lesions on same or lower dose of corticosteroids compared to baseline scan. Subjects should be on a corticosteroid dose that should not be greater than the dose at time of baseline scan, and should be stable or improved clinically.
 - Stable Disease (SD): This occurs if the subjects did not qualify for CR, PR, or progressive disease (PD) (see [below](#)). There should be stable or improved

- nonenhancing (T2/FLAIR) lesions on same or lower dose of corticosteroids compared to baseline scan. In the event that the corticosteroid dose has been increased, the last scan considered to show stable disease will be the scan obtained when the corticosteroid dose was equivalent to the baseline dose. The subject should be stable or improved clinically.
- Progressive Disease (PD): Progression is defined as >25% increase in sum of the products of perpendicular diameters of enhancing lesions (over baseline if no decrease) on stable or increasing doses of corticosteroids and/or a significant increase in T2/FLAIR non-enhancing lesion on stable or increasing doses of corticosteroids compared to baseline scan or best response following initiation of therapy, not due to co-morbid events. Any new lesion. Clear clinical deterioration not attributable to other causes apart from the tumor. Failure to return for evaluation due to death or deteriorating condition is considered progressive disease as well.

Reference:

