5.2 Study Subjects

5.2.1 Definitions of Analysis Sets

The following analysis sets will be defined:

- **Evaluable Analysis Set**, defined as all evaluable subjects, who have measurable disease present at baseline and at least 1 postbaseline efficacy assessment, unless they have discontinued prior to the first efficacy assessment due to progressive disease. Efficacy analyses in Phase 2 will primarily be based on the Evaluable Analysis Set.
- **Safety Analysis Set**, defined as all subjects who received at least 1 dose of study drug (lenvatinib or everolimus). This will be the analysis set for disposition, demographic and baseline characteristics, previous anticancer medications, prior and concomitant medications, procedures and radiotherapy, medical history, efficacy analysis in Phase 1 as well as all safety evaluations.
- **Pharmacokinetic (PK) Analysis Set**, defined as subjects in the Safety Analysis Set who had at least 1 measurable postdose plasma concentration with an adequately documented drug administration history.
- **Pharmacodynamic Analysis Set**, defined as all subjects in Safety Analysis Set who had evaluable pharmacodynamic data.

All analyses will be presented by planned dose level group in Phase 1 and separately for each study cohort in Phase 2, unless otherwise specified. A summary table and listing will also be provided to identify subjects in each analysis set.

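### Phase 2 subjects who die or decline before the first scan can be replaced instead of counted as failures, which tilts the Week 16 ORR modestly upward

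*Protocol*

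**What the plan says.** Protocol 9.7.1.2 limits the Evaluable Analysis Set to subjects with measurable disease at baseline and "at least 1 post-baseline efficacy assessment, unless they have discontinued prior to the first efficacy assessment due to progressive disease". Protocol 9.1, SAP 3.2 and SAP 5.2.1 repeat that condition. Protocol 9.1 adds: "Subjects who are not evaluable for objective response will be replaced".

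SAP 5.2.1 states: "Efficacy analyses in Phase 2 will primarily be based on the Evaluable Analysis Set". The word primarily suggests a second set, but SAP 13.2 lists Week 16 ORR on the Evaluable Analysis Set only.

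The reasons available for early discontinuation (Protocol 9.5.5) are "AE(s), lost to follow-up, subject choice, progression of disease, withdrawal of consent, pregnancy, study terminated by sponsor, or other". Death, clinical deterioration and lack of benefit have no code of their own, although Protocol 9.1.4 makes absence of clinical benefit a stopping criterion separate from objective progression.

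For high-grade glioma, Appendix 14 says: "Failure to return for evaluation due to death or deteriorating condition is considered progressive disease as well". For Ewing sarcoma and rhabdomyosarcoma, Appendix 1 adopts the published RECIST 1.1 guideline and says: "The sole modification to RECIST 1.1 to be implemented in this trial is that chest x-rays may not be used to follow disease". The protocol itself writes no rule for death or deterioration before a scan in those two cohorts.

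Protocol 9.7.1.6 and SAP 5.4.1.2 describe evaluability differently. Both require the disease to have been re-evaluated after baseline, and neither makes an exception for progression.

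**The concern.** Only confirmed CR or PR counts (Protocol 9.7.1.6.1), so a treated subject who is never scanned is certain to be a non-responder. Whether that subject stays in the denominator depends on the recorded reason for stopping. If the reason is progression, the subject is a failure. If it is subject choice, withdrawal or other, the subject leaves the count and is replaced by someone who may respond. The first scheduled Phase 2 scan is at Week 8, in recurrent or refractory disease, so such cases are plausible. The trial is open label and investigator assessed.

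Every such replacement moves the result in the drug's favour. It affects the ORR estimate, the 0-of-10 futility stop and the 3-of-20 success rule. The conflicting definition in 9.7.1.6 and SAP 5.4.1.2 adds a second problem: read literally, it drops even unscanned subjects who stopped for progression, in all three cohorts.

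**Working it through.** **Inputs.** Stop at 0 responses in 10; success needs at least 3 in 20; null 5%, alternative 25%; stated one-sided alpha 0.07 and power 88%; at most 22 enrolled per cohort for a 10% non-evaluable rate (Protocol 9.1 and 9.7.2, SAP 4). The fraction *d* of treated subjects who are unscanned non-responders and are replaced is an assumption.

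**The plan's own figure.** P(success) = Σ over x₁ = 1 to 10 of Bin(x₁; 10, p) × P(X₂ ≥ 3 − x₁), where X₂ ~ Bin(10, p). At p = 0.05:
- P(X₁ = 0) = 0.95¹⁰ = 0.5987, P(X₁ = 1) = 0.3151, P(X₁ = 2) = 0.0746, P(X₁ ≥ 3) = 0.0115
- P(X₂ ≥ 2) = 0.0861, P(X₂ ≥ 1) = 0.4013
- P(success) = 0.3151 × 0.0861 + 0.0746 × 0.4013 + 0.0115 = 0.0686

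At p = 0.25 the same sum is 0.882. Both stated figures reproduce.

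**Effect of replacement, no enrolment cap.** Removing a fraction *d*, all non-responders, gives an ORR among evaluable subjects of p/(1 − d). With d = 0.10, 0.05/0.90 = 0.0556. The sum above then gives 0.0879. The chance that a null cohort stops at 0 of 10 falls from 0.599 to (1 − 0.0556)¹⁰ = 0.565.

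**Effect with the 22-subject cap.** Let each treated subject be removed with probability d, respond with probability p, or be an evaluable non-responder with probability 1 − d − p. Stop at 10 evaluable with no response; otherwise continue to 20 evaluable or 22 treated, whichever comes first, and declare success at 3 or more responses. The documents do not say what happens if the cap is reached before 20 evaluable; applying the 3-response threshold there is an assumption. The exact recursion f(n, e, x) = d·f(n+1, e, x) + p·f(n+1, e+1, x+1) + (1 − d − p)·f(n+1, e+1, x), for n treated, e evaluable and x responders, gives at p = 0.05:

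| d (assumed) | P(success), cap 22 | P(success), no cap |
|---|---|---|
| 0 | 0.0686 | 0.0686 |
| 0.10 | 0.0824 | 0.0879 |
| 0.20 | 0.0886 | 0.1149 |

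A simulation of the capped rule at d = 0.10 gave about 8.3%, in line with the exact 8.2%. As a ceiling, P(at least 3 responders among 22 treated at 5%) = 0.095, whatever is removed.

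**Observed example.** Three responders with two unscanned failures replaced: 3/20 = 15.0% (exact 95% CI 3.2 to 37.9) is reported, against 3/22 = 13.6% (2.9 to 34.9) in all treated.

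**The case against.** Several provisions narrow the gap.
- Protocol 9.5.1.5.1 says "worsening of the primary disease should be captured under efficacy assessments as disease progression rather than as an AE", so disease-related decline should not be filed as an adverse event. The exception in 9.7.1.2 says progressive disease, not objective progression, so clinical progression can meet it.
- Protocol 9.5.1.3.1 continues scans every 12 weeks after a stop for another reason, until progression or a new agent. Protocol 9.4.7.2 treats additional anticancer therapy as evidence of progression.
- Protocol 9.3.3 records contributing reasons as well as the primary one, and the SAP lists analysis-set membership and deaths, so a reader could rebuild an all-treated ORR.
- Protocol 9.7.1.6.2 names early stops "including discontinuations due to toxicity, undocumented clinical progression, change of cancer treatment, or decreasing performance status" apart from recorded progression, but that is censoring text for duration of response. It concerns responders, who have already been scanned, and does not govern evaluability.

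All of this stands. It does not close the gap: the adverse-event instruction does not set the disposition reason, later scans cannot help a child who has died, and none of these provisions states how a sarcoma death before the first scan is counted.

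Two stronger readings are tempting. A reader might infer that the same early death is definitely a failure in the glioma cohort and definitely replaced in the sarcoma cohorts. The documents do not establish that. Appendix 14 defines a response category while 9.7.1.2 turns on the reason for stopping, no text links the two, and 9.7.1.6 has no progression exception even for glioma. The RECIST 1.1 guideline is adopted by citation and is not reproduced, so silence in Appendix 1 does not prove that no rule exists. A reader might also take 11.5% as the false-positive rate at 20% removed. Reaching 20 evaluable would then need on average 20/0.80 = 25 treated, above the cap of 22, and the rate cannot exceed 9.5%.

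**Conclusion.** The point holds in a limited form. As written, a Phase 2 subject who dies or declines before the first scan can leave the primary denominator according to how the stop is recorded, and two evaluability definitions conflict. The direction is certain wherever such a replacement occurs, because every removed subject is a non-responder.

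The size is modest: at most about 1.3 to 1.9 percentage points on the false-positive rate (6.9% to 8.2% capped, 8.8% uncapped) and about 1.4 points on the ORR at 3 responders. These are upper bounds. They assign the whole assumed 10% to early death or decline, whereas the planned allowance also covers loss to follow-up, withdrawal and true toxicity. The documents give no rate for early death or decline.

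**What to change.** Use one evaluability definition in Protocol 9.1, 9.7.1.2 and 9.7.1.6 and in SAP 3.2, 5.2.1 and 5.4.1.2, for all three cohorts. Under it, subjects who stop before the first scan because of progressive disease, death, or clinical deterioration or lack of benefit are non-responders and are not replaced.

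Add to SAP 13.2 the Week 16 ORR in all treated subjects with measurable disease, counting no scan as non-response, beside the Evaluable Analysis Set result. This row also shows the effect of the remaining replacements (for example loss to follow-up or toxicity without decline), which the new definition would still allow.

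The cost is definition wording, one extra row per cohort from data already collected, and a slightly lower reported ORR. No additional subjects are needed; replacements can only fall.
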